#### 4.4. End of Study Definition

A participant is considered to have completed the study if he or she has completed all required phases of the study including the last scheduled procedure shown in the SoA (Section 1.3).

Any participant who does not satisfy this definition but who has completed all the key assessments may be considered a completer at the discretion of the sponsor.

The end of the study is defined as the date of the last visit of the last participant in the study.

## 5. Study Population

Eligibility of participants for the study will be based on the results of screening medical history, physical examination, vital signs, clinical laboratory tests, and ECG.

The inclusion and exclusion criteria used to determine eligibility should be applied at screening only, and not continuously throughout the trial.

The nature of any conditions present at the time of the physical examination and any preexisting conditions will be documented.

Screening may occur up to 28 days prior to enrollment. Participants who are not enrolled within 28 days of screening may undergo an additional medical assessment and/or clinical measurements to confirm their eligibility. Parameters repeated for screening include clinical laboratory tests, body weight, ECGs, and vital signs.

Prospective approval of protocol deviations to recruitment and enrollment criteria, also known as protocol waivers or exemptions, is not permitted.

Individuals who do not meet the criteria for participation in this study (screen failure) may not be rescreened.

### 5.1. Inclusion Criteria

Participants are eligible to be included in the study only if all of the following criteria apply:

#### Age

1. Participant must be 21 to 65 years of age inclusive, at the time of signing the informed consent.

#### Type of participant and disease characteristics

2. Participants who are overtly healthy as determined through medical evaluation including screening medical history, physical examination, vital signs, clinical laboratory tests, and ECG.
3. Have clinical laboratory test results within normal reference range for the population or CRU, or results with acceptable deviations that are judged to be not clinically significant by the investigator.
4. Have venous access sufficient to allow blood sampling as per the protocol.
5. Are able and willing to consume the high-fat, high-calorie breakfast meal provided on dosing days (Part B only).
6. Are reliable and willing to make themselves available for the duration of the study and who will comply with the required study and dosing visits and abide by the clinical research site policy and procedure and study restrictions.

#### Weight

7. Body mass index within the range 19.0 to 40.0 kg/m^2 (inclusive), at screening.

**Sex and contraceptive/barrier requirements**

8. Males who agree to use highly effective/effective methods of contraception may participate in this trial. Please refer to Appendix 4 for definitions and additional guidance related to contraception.
9. Only women not of childbearing potential (WNOCBP) may participate in this trial

Contraceptive use by participants should be consistent with local regulations regarding the methods of contraception for those participating in clinical studies. For the contraception requirements of this protocol, see Appendix 10.4.

**Informed consent**

10. Capable of giving signed informed consent as described in Appendix 1, which includes compliance with the requirements and restrictions listed in the ICF and in this protocol.

**5.2. Exclusion Criteria**

Participants are excluded from the study if any of the following criteria apply:

**Medical conditions**

11. Have a history of atopy (severe or multiple allergic manifestations) or clinically significant multiple or severe drug allergies, or intolerance to topical corticosteroids, or severe posttreatment hypersensitivity reactions (including, but not limited to, erythema multiforme major, linear immunoglobulin A dermatosis, toxic epidermal necrolysis, anaphylaxis, angioedema, or exfoliative dermatitis).
12. Have a significant history of or current CV (for example, myocardial infarction, congestive heart failure, cerebrovascular accident, venous thromboembolism, etc.), respiratory, renal, GI (including involving the liver, gallbladder or gallbladder surgery), endocrine, hematological (including history of thrombocytopenia), or neurological disorders capable of significantly altering the absorption, metabolism, or elimination of drugs; of constituting a risk while taking the IP; or of interfering with the interpretation of data.
13. Have a mean supine HR less than 45 bpm or greater than 100 bpm from 2 assessments at screening. If a repeat measurement (mean of 2 assessments) shows values within the range of 45 to 100 bpm, the participant may be included in the trial.
14. Have a mean supine systolic BP higher than 160 mmHg and a mean supine diastolic BP higher than 95 mmHg from 2 assessments at screening; therefore, if a repeat measurement (mean of 2 assessments) shows values within the range (systolic BP  $\leq$  160 mmHg and /or diastolic BP  $\leq$  95 mmHg), the participant can be included in the trial.
15. Have undergone any form of bariatric surgery.
16. Have a history of GI bleeding, or gastric or duodenal ulcers.
17. Have a personal or family history of medullary thyroid carcinoma or multiple endocrine neoplasia syndrome type 2.

18. Have a history of acute or chronic pancreatitis, or elevation in serum lipase and/or amylase levels greater than 1.5 times the ULN.
19. Have clinical signs or symptoms of liver disease, acute or chronic hepatitis.
20. Have evidence of significant active neuropsychiatric disease as determined by the investigator.

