### 2.3. Benefit/Risk Assessment

There is no anticipated therapeutic benefit for the participants in this trial.

The sponsor has evaluated the preclinical and clinical risks associated with LY3493269. Nonclinical safety of SC LY3493269 was evaluated in a CV safety pharmacology study in monkeys and 1-month repeat-dose toxicology studies in rats and monkeys. Important LY3493269-related findings in the rat and monkey included body weight loss and/or reduced body weight gain and decreased food consumption. Additional findings from the monkey studies included changes in CV parameters (such as increases in HR and BP). In the completed clinical studies where LY3493269 was administered SC (Studies GZHA and GZHC) or orally with C10 (Study GZHB) or SNAC (Study GZHF), similar findings were observed, which include

- nausea
- vomiting
- loss of appetite, and
- increased HR.

SNAC has generally regarded as safe status and is contained in FDA-approved medical food (Eligen®-Vitamin B12, Emisphere, Roseland, NJ, USA; Twarog et al. 2019). Rybelsus® tablet, which is approved by FDA, European Medicines Agency and Japan Pharmaceuticals and Medical Devices Agency, also contains SNAC (daily dose of 300 mg). In addition, in a first-in-human trial, up to 600 mg SNAC was evaluated with oral semaglutide with no safety concerns reported (Granhall et al. 2019).

C10 has a long history of use in humans and has food additive status in the US and EU with no daily limits on consumption (Twarog et al. 2019). In the completed nonclinical safety pharmacology and toxicology studies, LY3493269 orally co-administered with C10, produced increased HR, body weight loss and/or decreased body weight gain, and decreased food consumption, which are consistent with, or secondary to, incretin pharmacology. The effects on body weight were dose limiting and resulted in dosing suspension at the highest dose levels tested in monkeys. No adverse C10-related effects were observed up to 350 mg/kg in any of the toxicology studies/assessments.

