**Other exclusions**

30. Are Site personnel directly affiliated with this study and their immediate families.  
Immediate family is defined as a spouse, biological or legal guardian, child, or sibling
31. Are Lilly employees.
32. Have previously completed or withdrawn from this study.
33. Have donated blood of more than 450 mL or have participated in a clinical study that required similar blood volume withdrawn within the past 3 calendar months.
34. Women who are lactating.
35. Women of childbearing potential
36. Have known allergies to LY3493269, related compounds, or any components of the formulation (including C10 or SNAC), or a history of significant atopy.
37. Regularly use known drugs of abuse.
38. Have an average weekly alcohol intake that exceeds 21 units per week (males) and 14 units per week (females) or are unwilling to stop alcohol consumption as required during the study (1 unit = 12 oz or 360 mL of beer; 5 oz or 150 mL of wine; 1.5 oz or 45 mL of distilled spirits).
39. Smoke >10 cigarettes per day or the equivalent or are unable or unwilling to refrain from nicotine during CRU admission.
40. Are unwilling to comply with the dietary restrictions required for this study.
41. In the opinion of the investigator or sponsor, are unsuitable for inclusion in the study.

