#### **8.2.2. Vital Signs**

For each participant, vital sign measurements should be conducted according to the SoA (Section 1.3) and as clinically indicated.

Vital sign measurements should be obtained before collection of blood samples (applicable for study visits).

BP and pulse rate should be measured after at least 5 minutes in a supine position.

Note: If white-coat hypertension is suspected at screening, the participant can be included in the trial if a repeated measurement (a mean of 2 measurements) shows values within the acceptable range.

If orthostatic measurements are required, participants should be supine for at least 5 minutes and stand for at least 2 minutes. If the participant feels unable to stand, only supine vital signs will be recorded.

Unscheduled orthostatic vital signs should be assessed, if possible, during any AE of dizziness or posture-induced symptoms. Additional vital signs may be measured during each study period if warranted.

Body temperature will be measured, as specified in the SoA (Section 1.3), and as clinically indicated.

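### Minor: exclusion criterion 14 joins its two blood pressure limits with *and*, so by itself it does not exclude an isolated high systolic or diastolic pressure of any size

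*Protocol*

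**What the plan says.** Criterion 14 in Protocol 5.2 excludes participants who "Have a mean supine systolic BP higher than 160 mmHg and a mean supine diastolic BP higher than 95 mmHg", each the mean of two screening assessments. It then allows inclusion "if a repeat measurement (mean of 2 assessments) shows values within the range (systolic BP" at most 160 mmHg *and /or* diastolic at most 95 mmHg).

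The white-coat note in Protocol 8.2.2 says that "the participant can be included in the trial if a repeated measurement (a mean of 2 measurements) shows values within the acceptable range", but gives no figures for that range. The discontinuation rules in Protocol 7.1 have a QTcF threshold and no blood pressure threshold. SAP 10.4.6 analyses change in blood pressure but sets no limit.

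Three other criteria leave room for judgment, none with a blood pressure number:

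- Inclusion criterion 2: "Participants who are overtly healthy as determined through medical evaluation including screening medical history, physical examination, vital signs", among other evaluations. It is mandatory: "Participants are eligible to be included in the study only if all of the following criteria apply".
- Exclusion criterion 12: a significant cardiovascular (or other listed) disorder capable "of constituting a risk while taking the IP".
- Exclusion criterion 41: those who, "In the opinion of the investigator or sponsor, are unsuitable for inclusion in the study".

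**The concern.** A numeric limit is there so that entry does not rest on judgment alone. With *and* between the two limits, criterion 14 acts only when both pressures are high. Isolated systolic or isolated diastolic elevation passes it, however large. The *and /or* in the repeat clause adds a second difficulty, because two readers could decide the same repeat reading differently.

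What is at stake is participant safety. Protocol 2.3 states that "There is no anticipated therapeutic benefit for the participants in this trial" and lists cardiovascular effects among the potential risks of the oral drug. The criteria admit ages up to 65 and BMI up to 40 kg/m² (Protocol 5.1, criteria 1 and 7), so a raised screening pressure is plausible. They are applied at screening only (Protocol 5), so no numeric entry limit is applied again on Day 1.

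**Working it through.** There is no sample size, power or error-rate figure to reproduce. The check is one of logic. Write S for mean supine systolic and D for mean supine diastolic pressure, in mmHg.

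**Rules, from Protocol 5.2, criterion 14**

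- Current trigger: exclude if S > 160 and D > 95.
- Repeat clause, inclusive reading of *and /or*: admit if S ≤ 160 or D ≤ 95.
- Repeat clause, strict reading: admit if S ≤ 160 and D ≤ 95.
- Proposed trigger: exclude if S > 160 or D > 95. Proposed repeat: admit only if S ≤ 160 and D ≤ 95.

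**First assessment.** The repeat clause plays no part here, so the result is the same under either reading of it.

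| Mean BP | S > 160? | D > 95? | Current criterion 14 | Proposed |
|---|---|---|---|---|
| 150/90 | no | no | not excluded | not excluded |
| 160/95 | no | no | not excluded | not excluded |
| 161/96 | yes | yes | excluded | excluded |
| 185/92 | yes | no | not excluded | excluded |
| 220/80 | yes | no | not excluded | excluded |
| 150/110 | no | yes | not excluded | excluded |

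Only isolated elevations change. The limits themselves stay where they are.

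**Repeat measurement.** Take a first reading of 175/100 and a repeat of 175/94.

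- First reading: 175 > 160 and 100 > 95, so excluded pending a repeat.
- Repeat, inclusive reading: 94 ≤ 95, so readmitted.
- Repeat, strict reading: 175 > 160, so not readmitted. Yet 175/94 as a first reading would not have been excluded, so on this reading the two halves of the criterion disagree.
- Repeat, proposed wording: 175 > 160, so not readmitted. This agrees with the proposed trigger.

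The negation of *S > 160 and D > 95* is *S ≤ 160 or D ≤ 95*. The inclusive reading is therefore the exact complement of the current trigger, and the criterion is then self-consistent but lenient. Under the strict reading it is inconsistent for every isolated elevation.

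**Any other limit?** No other mmHg limit appears in either document. The range in Protocol 8.2.2 can only refer back to criterion 14.

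These are outcomes of criterion 14 alone, not of the whole eligibility section.

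**The case against.** The best defence is that the rule may be intended. On the inclusive reading the trigger and the repeat clause are exact complements, which points away from a slip in one word. Nothing in the documents shows that isolated elevation was meant to be excluded. The *or* in criterion 13 (heart rate) is no precedent, since it joins the two ends of one variable. This stands as far as intent goes. But no reason is given for the rule, and a deliberate *and* would still leave each pressure without a ceiling of its own.

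The second defence is that other provisions cover such volunteers. Criteria 2, 12 and 41 allow refusal, and all screening evaluations must be reviewed before eligibility is confirmed (Protocol 8). Volunteers on antihypertensives also meet the concomitant-drug restriction (Protocol 6.8), although that does not reach untreated hypertension. This is correct, and it is why enrolment of someone at 185/92 is possible rather than assured. It does not supply a number.

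Third, the evidence of harm is thin. Blood pressure increases are reported in monkeys dosed subcutaneously. The cardiovascular finding listed in people is increased heart rate (Protocol 2.3), which already has a numeric exclusion in criterion 13. Dosing is three 4-mg doses, with exposure expected to be well below that of the subcutaneous multiple-dose study (Protocol 4.3). Blood pressure is checked predose and at 1, 4 and 12 hours on each dosing day (Protocol 1.3). The inpatient stay can be extended (Protocol 2.3), and the investigator can stop dosing for safety (Protocol 7.1). All of this stands and keeps the point minor. These measures detect or manage a rise but do not set who may enter.

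**Conclusion.** The point holds as a minor one. Taken literally and alone, criterion 14 does not exclude an isolated systolic pressure above 160 mmHg or an isolated diastolic pressure above 95 mmHg, and no other numeric limit in the protocol or SAP does so. That conclusion does not depend on how *and /or* is read. The readmission of 175/94 after 175/100 does: it follows from the inclusive reading only.

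The number of people affected is unknown, because the documents give no screening blood pressure distribution. With a target of about 10 completers per group it may be small or zero. The AUC and Cmax comparisons, the sample size and the analysis methods are untouched. Confidence is medium, because the *and* may be deliberate and judgment-based criteria can catch the same volunteers.

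**What to change.** Reword criterion 14 to exclude a participant if mean supine systolic pressure is above 160 mmHg **or** mean supine diastolic pressure is above 95 mmHg, each from two screening assessments. Allow inclusion on a repeat (mean of two assessments) only if systolic is at most 160 mmHg **and** diastolic is at most 95 mmHg. Optionally, point the white-coat note in Protocol 8.2.2 to criterion 14. If the present rule is intended, say why and set an upper cap for each pressure alone. The documents give no basis for a value, so the sponsor would have to choose one.

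The cost is one sentence, plus the optional cross-reference, and IRB/IEC approval of the amendment (Protocol 10.1.1). A few more volunteers may fail screening, and screen failures may not be rescreened (Protocol 5 and 5.4). Keeping the repeat measurement limits that loss. Part B has been cancelled (SAP 5 and 12), and the documents do not say whether Part A enrolment is complete, so the change may matter only for remaining enrolment or for reuse of the criterion in later protocols.

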#### **Prior/concomitant therapy**

21. Have been treated with prescription drugs that promote weight loss within 3 months prior to screening. Examples include
  - Meridia® (sibutramine)
  - Sanorex® (mazindol)
  - Adipex-P® (phentermine)
  - BELVIQ® (lorcaserin)
  - Mysimba® (naltrexone/bupropion)
  - Saxenda® (liraglutide), or
  - similar other body weight loss medications including any over-the-counter medications or supplements (for example, alli®).
22. Have received chronic (lasting >14 consecutive days) systemic glucocorticoid therapy in the past year, or have received any glucocorticoid therapy within 1 month before screening (topical, intra-articular, and inhaled preparations such as steroid nasal spray are permitted in the study).

#### **Prior/concurrent clinical study experience**

23. Are currently enrolled in a clinical study involving an IP or any other type of medical research judged not to be scientifically or medically compatible with this study.
24. Have participated within the past 30 days of screening in a clinical study involving an IP; at least 5 half-lives or 30 days, whichever is longer, should have passed.

#### **Diagnostic assessments**

25. Have an abnormality in the 12-lead ECG at screening that, in the opinion of the investigator, increases the risks associated with participating in the study or may confound ECG (QT) data analysis, such as a QTcF >450 msec for males and >470 msec for females, short PR interval (<120 msec), or PR interval >220 msec, second- or third-degree atrioventricular block, intraventricular conduction delay with QRS >120 msec, right bundle branch block, left bundle branch block or Wolff-Parkinson-White syndrome.
26. Have serum AST or ALT >1.5x ULN or TBL >1.5x ULN.
27. Show evidence of human immunodeficiency virus infection and/or positive human immunodeficiency virus antibodies.
28. Show evidence of hepatitis C and/or positive hepatitis C antibody.
29. Show evidence of hepatitis B, positive hepatitis B core antibody, and/or positive hepatitis B surface antigen.

**Other exclusions**

30. Are Site personnel directly affiliated with this study and their immediate families.  
Immediate family is defined as a spouse, biological or legal guardian, child, or sibling
31. Are Lilly employees.
32. Have previously completed or withdrawn from this study.
33. Have donated blood of more than 450 mL or have participated in a clinical study that required similar blood volume withdrawn within the past 3 calendar months.
34. Women who are lactating.
35. Women of childbearing potential
36. Have known allergies to LY3493269, related compounds, or any components of the formulation (including C10 or SNAC), or a history of significant atopy.
37. Regularly use known drugs of abuse.
38. Have an average weekly alcohol intake that exceeds 21 units per week (males) and 14 units per week (females) or are unwilling to stop alcohol consumption as required during the study (1 unit = 12 oz or 360 mL of beer; 5 oz or 150 mL of wine; 1.5 oz or 45 mL of distilled spirits).
39. Smoke >10 cigarettes per day or the equivalent or are unable or unwilling to refrain from nicotine during CRU admission.
40. Are unwilling to comply with the dietary restrictions required for this study.
41. In the opinion of the investigator or sponsor, are unsuitable for inclusion in the study.

**5.3. Lifestyle Considerations**

Throughout the study, participants may undergo medical assessments and review of compliance with requirements before continuing in the study.

**5.3.1. Meals and Dietary Restrictions**

All participants will observe an overnight fast of at least 8 hours prior to the scheduled dosing time and for each subsequent study day when clinical safety laboratory fasting samples are taken.

Further requirements on water and meal restrictions related to administration of study intervention are found in Section [6.1](#).

Throughout the inpatient period, apart from the high-fat, high-calorie meal served at dosing, and the standardized breakfast meal for Treatment B2 [dosing condition B2(b)], standard meals will be administered in the CRU. While not resident in the CRU, participants will be encouraged to follow their normal diet.

**5.3.1.1. High-Fat, High-Calorie Breakfast**

For Treatments B1 and B2, participants may receive study intervention in the fed state. A high-fat, high-calorie breakfast will be served to participants prior to dosing to achieve a fed state.

Participants will be encouraged to finish the meal, including milk or milk substitute. The amount of the meal consumed by the participant will be documented by the CRU.

The high-fat, high-calorie breakfast should consist of approximately 800 to 1000 calories. This meal derives approximately 150, 250, and 500 to 600 calories from protein, carbohydrates, and fat, respectively. At least approximately 50% of the calories should be derived from fat. An example of a high-fat, high-calorie breakfast is as follows:

- two eggs fried in butter
- two strips of bacon
- two slices of toast with butter
- four ounces of hash brown potatoes, and
- 240 mL of whole milk or substitute.

Appropriate substitutions of meal components that match the fat- and calorie-content may be made to accommodate an individual participant's dietary restrictions or requirements.

Participants will receive each dose with approximately 240 mL of water.

### **5.3.1.2. Standardized Breakfast**

Under dosing conditions in Treatment B2(b) as described in [Table GZHI.6.1](#), a standardized breakfast will be served 30 minutes after dosing. This meal should consist of approximately 558 calories, composed of approximately 49% carbohydrate, 34% fat, and 17% protein.

Apart from the restrictions listed above and in [Table GZHI.6.1](#), there are no other beverage restrictions. Water ad libitum is allowed only until 1 hour before dosing and following the 2-hour postdose fast.

Further requirements on water and timing of the high-fat, high-calorie breakfast and standardized breakfast meals are found in Section [6.1](#).

